**Table 2.8-2 CTCAE grades for laboratory parameters to be analyzed**

CTCAE Term	Grade 1	Grade 2	Grade 3	Grade 4
HGB decreased (Anemia)	<LLN - 100 g/L	<100 - 80 g/L	<80 g/L	
Platelet count decreased	<LLN - 75.0 x10e9 /L	<75.0 - 50.0 x10e9 /L	<50.0 - 25.0 x10e9 /L	<25.0 x 10e9 /L
White blood cell decreased	<LLN - 3.0 x 10e9 /L	<3.0 - 2.0 x 10e9 /L	<2.0 - 1.0 x 10e9 /L	<1.0 x 10e9 /L
Neutrophil count decreased	<LLN - 1.5 x 10e9 /L	<1.5 - 1.0 x 10e9 /L	<1.0 - 0.5 x 10e9 /L	<0.5 x 10e9 /L
Lymphocyte count decreased	<LLN - 0.8 x 10e9/L	<0.8 - 0.5 x 10e9 /L	<0.5 - 0.2 x 10e9 /L	<0.2 x 10e9 /L
Creatinine increased*	>1 - 1.5 x baseline; baseline; >ULN - 1.5 x ULN	>1.5 - 3.0 xULN	>3.0 baseline; >3.0 - 6.0 x ULN	>6.0 x ULN
TBL increased	>ULN - 1.5 x ULN	>1.5 - 3.0 x ULN	>3.0 - 10.0 x ULN	>10.0 x ULN
GGT increased	>ULN - 2.5 x ULN	>2.5 - 5.0 x ULN	>5.0 - 20.0 x ULN	>20.0 x ULN
ALT increased	>ULN - 3.0 x ULN	>3.0 - 5.0 x ULN	>5.0 - 20.0 x ULN	>20.0 x ULN
AST increased	>ULN - 3.0 x ULN	>3.0 - 5.0 x ULN	>5.0 - 20.0 x ULN	>20.0 x ULN
ALP increased	>ULN - 2.5 x ULN	>2.5 - 5.0 x ULN	>5.0 - 20.0 x ULN	>20.0 x ULN

Glucose increased (Hyperglycemia)	>ULN - 8.9 mmol/L	>8.9 - 13.9 mmol/L	>13.9 - 27.8 mmol/L	>27.8 mmol/L
Glucose decreased (Hypoglycemia)	<LLN - 3.0 mmol/L	<3.0 - 2.2 mmol/L	<2.2 - 1.7 mmol/L	<1.7 mmol/L
Cholesterol high Hypertriglyceridem ia	mmol/L 1.71 - 3.42 mmol/L	>7.75 - 10.34 mmol/L >3.42 - 5.7mmol/L	mmol/L >5.7 - 11.4 mmol/L	>12.92 mmol/L >11.4 mmol/L

\*Note: for "creatinine increased" the baseline criteria do not apply

Shift tables will be presented comparing baseline laboratory result (CTCAE grade) with the worst results (expressed in CTCAE grade) during the treatment phase (either initial or entire) analyzed. Of note, baseline will be defined as last assessment prior to first dosing in initial treatment phase. Patients with abnormal laboratory values will be listed and values outside the normal ranges will be flagged.

Summaries for newly occurring or worsening clinically notable lipid abnormalities will also be provided cumulatively for each of the following parameters and categories:

- HDL:
  - $\leq LLN$
  - $<0.8 \times LLN$
- LDL, cholesterol, triglycerides:
  - $\geq ULN$
  - $>1.5 \times ULN$
  - $>2.5 \times ULN$

Newly occurring or worsening liver enzyme abnormalities will also be summarized based on the event criteria given in Table 2.8-3:

**Table 2.8-3 Liver-related events**

Parameter	Criterion
ALT	$>3 \times ULN$ ; $>5 \times ULN$ ; $>8 \times ULN$ ; $>10 \times ULN$ , $>20 \times ULN$
AST	$>3 \times ULN$ ; $>5 \times ULN$ ; $>8 \times ULN$ ; $>10 \times ULN$ ; $>20 \times ULN$
ALT or AST	$>3 \times ULN$ ; $>5 \times ULN$ ; $>8 \times ULN$ ; $>10 \times ULN$ ; $>20 \times ULN$
TBL	$>1.5 \times ULN$ , $>2 \times ULN$ , $>3 \times ULN$ ,
ALP	$>2 \times ULN$ , $>3 \times ULN$ , $>5 \times ULN$
ALT or AST & TBL	ALT or AST $>3 \times ULN$ & TBL $>2 \times ULN$ ; ALT or AST $>5 \times ULN$ & TBL $>2 \times ULN$ ; ALT or AST $>8 \times ULN$ & TBL $>2 \times ULN$ ; ALT or AST $>10 \times ULN$ & TBL $>2 \times ULN$
ALP & TBL	ALP $>3 \times ULN$ & TBL $>2 \times ULN$ ALP $>5 \times ULN$ & TBL $>2 \times ULN$

ALT or AST & TBL & ALP	ALT or AST>3xULN & TBL >2xULN & ALP<2xULN (Hy's Law)  Note: elevated ALP may suggest obstruction as a consequence of gall bladder or bile duct disease; ALP may also be increased in malignancy. FDA therefore terms Hy's Law cases as indicators of pure hepatocellular injury. This does not mean that cases of ALT or AST >3xULN & TBL >2xULN & ALP $\geq$ 2xULN may not result in severe DILI.

Notes:
 
1) In studies which enroll patients with pre-existing liver disease, baseline LFT may be increased above ULN; in such a case it is meaningful to add the condition "and worse than baseline" to the abnormality criteria.
	

For a combined criterion to be fulfilled, all conditions have to be fulfilled on the same visit. The criteria are not mutually exclusive, e.g. a subject with ALT = 6.42xULN is counted for ALT >3xULN and ALT>5x ULN.

Individual subject data listings will be provided for patients with abnormal laboratory data. Data of patients with newly occurring or worsening liver enzyme abnormalities will be listed in an additional listing.

## 2.8.4 Other safety data

### 2.8.4.1 ECG and cardiac imaging data

The following quantitative variables will be summarized: ventricular rate, RR interval, PR interval, QRS duration, QT interval, and corrected QT interval (QTc). Both Bazett (QTcB) and Fridericia (QTcF) corrections will be presented for QTc.

QTc will be summarized by computing the number and percentage of patients (including 95%confidence intervals for pooled analyses, e.g. DMC or SCS) with:

- QTc > 500 msec
- QTc > 480 msec
- QTc > 450 msec
- QTc changes from baseline > 30 msec
- QTc changes from baseline > 60 msec
- PR > 250 msec

Summary statistics will be presented for ECG variables by visit and treatment group.

In addition, shift tables comparing baseline ECG interpretation (normal, abnormal, not available, total) with the worst on-study interpretation (normal, abnormal, not available, total) will be provided.

A listing of all newly occurring or worsening abnormalities will be provided, as well as a by-subject listing of all quantitative ECG parameters.

#### 2.8.4.2 Vital signs

Analysis in vital sign measurement using descriptive summary statistics for the change from baseline for each post-baseline visit will be performed. These descriptive summaries will be presented by vital sign and treatment group. Change from baseline will only be summarized for patients with both baseline and post-baseline values and will be calculated as:

$$\text{change from baseline} = \text{post-baseline value} - \text{baseline value}$$

The number and percentage of patients with newly occurring notable vital signs will be presented. Criteria for notable vital sign abnormalities are provided in Table 2.8-4 below.

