- 15. Underlying metabolic, hematologic, renal, hepatic, pulmonary, neurologic, endocrine, cardiac, infectious or gastrointestinal conditions which in the opinion of the investigator immunocompromises the patient and/or places the patient at unacceptable risk for participation in an immunomodulatory therapy.
- 16. Significant medical problems or diseases, including but not limited to the following: uncontrolled hypertension (≥ 160/95 mmHg), congestive heart failure (New York Heart Association status of class III or IV), and uncontrolled diabetes.
- 17. History of clinically significant liver disease or liver injury as indicated by abnormal liver function tests (LFT) such as aspartate aminotransferase/serum glutamic oxaloacetic transaminase (AST/SGOT), alanine aminotransferase/ serum glutamic pyruvic transaminase (ALT/SGPT), alkaline phosphatase, or serum bilirubin. The investigator should be guided by the following criteria:
 - Any single parameter may not exceed 2 × ULN. A single parameter elevated up to and including 2 × ULN should be re-checked once more as soon as possible, and in all cases, at least prior to enrollment/randomization, to rule out laboratory error.
 - If the total bilirubin concentration is increased above $2 \times ULN$, total bilirubin should be differentiated into the direct and indirect reacting bilirubin. In any case, serum bilirubin should not exceed the value of 1.6 mg/dL (27 μ mol/L).
- 18. History of renal trauma, glomerulonephritis, or patients with 1 kidney only, or a serum creatinine level exceeding 1.5 mg/dL (132.6 μmol/L).
- 19. Screening total white blood cell (WBC) count < 3000/μL, or platelets < 100000/μL or neutrophils < 1,500/μL or hemoglobin < 8.5 g/dL (85 g/L).
- 20. Active systemic infections during the last 2 weeks (exception: common cold) prior to randomization.
- 21. History of ongoing, chronic or recurrent infectious disease or evidence of tuberculosis infection as defined by a positive QuantiFERON TB-Gold test. Patients with a positive test may participate in the study if further work up (according to local practice/guidelines) establishes conclusively that the patient has no evidence of active tuberculosis. If presence of latent tuberculosis is established then treatment according to local country guidelines must have been initiated.
- 22. Known infection with human immunodeficiency virus (HIV), hepatitis B or hepatitis C at screening or randomization.

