**Table 2.8-4 Criteria for notable vital sign abnormalities**

Vital sign (unit)	Notable abnormalities
Systolic blood pressure (mmHg)	$\geq 140 \text{ mmHg}$ or $< 90 \text{ mmHg}$
Diastolic blood pressure (mmHg)	$\geq 90 \text{ mmHg}$ or $< 60 \text{ mmHg}$
Pulse (bpm)	$> 100 \text{ bpm}$ or $< 60 \text{ bpm}$

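### The vital-sign count of newly notable values cannot register a further rise in patients who enter with SBP 140-159 or DBP 90-94, and no other planned output counts such rises by arm

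*SAP*

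**What the plan says.** SAP 2.8.4.2 plans two analyses of vital signs. The first is descriptive: "Analysis in vital sign measurement using descriptive summary statistics for the change from baseline for each post-baseline visit will be performed", by vital sign and treatment group, for every patient who has both values. Under the general rule in SAP 2.1, continuous variables are summarised with the minimum and maximum as well as the mean, SD and median. The second is categorical: "The number and percentage of patients with newly occurring notable vital signs will be presented". SAP Table 2.8-4 supplies the criteria, with one high and one low limit per parameter: SBP 140 or above, or below 90; DBP 90 or above, or below 60. The term 'newly occurring' is not defined, and the denominator of the percentage is not stated.

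Protocol 4.2, exclusion criterion 16, sets the entry limit at "uncontrolled hypertension (≥ 160/95 mmHg".

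The laboratory section of the SAP uses a wider rule. For liver tests: "Newly occurring or worsening liver enzyme abnormalities will also be summarized", against the graded tiers of Table 2.8-3. The lipid summary is worded in the same way and also has tiers. For ECG the wider wording applies to a listing: "A listing of all newly occurring or worsening abnormalities will be provided".

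**The concern.** The entry limit lies above the notable threshold. Patients in the gap between them are eligible and are already notable when treatment starts. A count restricted to new occurrences, with no higher tier, has nothing left for them to cross. They are the patients with the highest blood pressure in the trial, and a threshold count is normally the output that shows how many individuals per arm had a marked rise. In this plan the count records a 1 mmHg step across the threshold and ignores a 45 mmHg rise above it.

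The denominator adds a smaller difficulty. If the percentage is taken over all patients, those who cannot have an event dilute it.

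**Working it through.** The documents give no figure on this point, so there is none to reproduce. The check is one of logic, followed by an illustration of size.

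**Inputs.** Notable high limits: SBP 140, DBP 90 (SAP Table 2.8-4; same limits in Protocol 6.5.2). Entry limit: 160/95 (Protocol 4.2, criterion 16), read as excluding a patient when either component reaches its limit. If both had to be reached, the eligible range would be wider. Baseline: the last value before first dose (SAP 2.1.1).

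**Step 1: who is already notable at entry.** SBP from 140 to 159, or DBP from 90 to 94.

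**Step 2: what the count can register.** A newly occurring high value requires baseline below the limit and a later value at or above it. Two readings were coded: not notable in either direction at Baseline, and direction-specific. Every integer rise was enumerated from SBP 140-159 (up to 260) and from DBP 90-94 (up to 160). Under both readings, none is counted for that parameter. Examples:

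| Parameter | Baseline to later value | Change | Counted as a new high value? |
|---|---|---|---|
| SBP | 139 to 140 | +1 | yes |
| SBP | 155 to 200 | +45 | no |
| SBP | 150 to 190 | +40 | no |
| DBP | 85 to 105 | +20 | yes |

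The last two rows could be one patient going from 150/85 to 190/105, missed on systolic and counted on diastolic. The block is per parameter, not per patient.

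**Step 3: what the other vital-sign summary shows.** These patients are all in the change-from-baseline table. With about 100 patients per arm, one rise of 45 mmHg moves the arm mean by 45/100 = 0.45 mmHg and appears as the maximum at that visit if nobody rose more. If a share s of the arm rises by r, the mean moves by s × r: 0.10 × 10 = 1 mmHg up to 0.30 × 40 = 12 mmHg (s and r are assumed). Neither the mean nor the maximum tells the reader how many patients rose.

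**Step 4: how many patients could be affected.** The documents give no baseline blood-pressure distribution. Assume normal SBP with mean μ and SD σ, truncated below 160:

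share at 140 or more = [Φ((160−μ)/σ) − Φ((140−μ)/σ)] / Φ((160−μ)/σ)

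- μ = 125, σ = 14: (0.9938 − 0.8580) / 0.9938 = 0.137
- μ = 130, σ = 15: (0.9772 − 0.7475) / 0.9772 = 0.235
- μ = 135, σ = 15: (0.9522 − 0.6306) / 0.9522 = 0.338

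That is about 14 to 34 patients in an arm of 100. No comparable figure is offered for DBP.

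**Step 5: dilution, if all patients are in the denominator.** With an assumed 10% incidence among patients able to have an event, the reported figure would be 10% × (1 − 0.137) = 8.6% down to 10% × (1 − 0.338) = 6.6%. Under randomisation the expected dilution is the same in both arms.

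**The case against.** The strongest reply is that these rises are not lost. The patients are in the change-from-baseline summaries with the maximum reported, and the other blood-pressure component can still be counted. Under Protocol 7.1 an abnormal result that is clinically significant, causes symptoms or needs therapy is an adverse event, and SAP 2.8.1 treats a pre-existing event that increases in severity as treatment-emergent, so worsening hypertension can be tabulated by arm. The protocol itself (9.5.2.3) asks only for change from baseline; the notable count is an addition. All of this stands, and it keeps the point small. It does not supply the missing count: a maximum shows one patient, and adverse-event reporting rests on the investigator's judgement of each case.

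SAP Table 2.8-1 also lists a crude incidence of notable vital signs without restricting it to new occurrences. If that is a separate table counting any notable post-baseline value, a patient going from 150 to 190 would appear in it, but so would one who stays at 150. It would not identify rises either.

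One might also infer that Table 2.8-4, by putting high and low limits in one cell, prevents a patient with high baseline SBP from being counted on falling below 90. That table lists criteria and is not an output layout, and Protocol 6.5.2 defines hypertension and hypotension separately. Direction-specific counting is equally compatible with the text, so this is an ambiguity to settle and not an error shown.

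Nor does the ECG section count abnormalities on the wider rule. Its wording there governs a listing, so the sound comparison is with lipids and liver tests.

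**Conclusion.** The gap is real and minor. On the usual meaning of the undefined term 'newly occurring', the count in SAP 2.8.4.2 cannot register a further rise in a blood-pressure component already notable at Baseline, and the eligibility criteria admit such patients. No planned output counts, by arm, patients whose measured blood pressure rises substantially from that starting point.

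A reader might infer that these patients can never show a rise anywhere in the report, or that this table is the only categorical comparison of blood pressure with placebo. The documents support neither. The by-visit summaries include these patients, and adverse-event tables by preferred term may capture clinically significant worsening. The supportable statement is that this is the only planned threshold-based count of measured blood pressure.

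The logical gap needs no distributional assumption. Its size does: the 14-34% for SBP depends wholly on the assumed means and SDs, and the true share is unknown from the documents. The primary analysis and the safety monitoring of patients are not affected.

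**What to change.** In SAP 2.8.4.2:

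- Define 'newly occurring' by direction and report high and low values in separate rows.
- Take each percentage over patients who are not notable in that direction at Baseline and who have a post-baseline value, and state that denominator.
- Add a shift table by arm of baseline category against worst post-baseline category, with a higher tier. For example: SBP below 90, 90-139, 140-159, 160 or above; DBP below 60, 60-89, 90-94, 95 or above. Take the worst value separately for the high and low directions. The upper cut-points borrow the figures in exclusion criterion 16 as analysis categories only and imply no clinical rule.
- If the term 'or worsening' is added to match the liver and lipid wording, define it as a move to a higher tier. With the present single high tier it would have no clear meaning, and a step from 150 to 151 could qualify.

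The cost is SAP wording and a few table rows. The data are already planned for the clinical database: Protocol Table 6-1 marks vital signs for database entry at Baseline, Weeks 8, 16, 24, 36 and 52, and at unscheduled visits. Weeks 2, 4, 12 and 20 are source-only, so a footnote should say that the worst value is taken over the recorded visits. Any higher cut-point remains arbitrary at its edge (158 to 160 changes category, 140 to 159 does not), but the table would then show by arm how many patients moved up a tier.

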**Table 2.8-4 Criteria for notable vital sign abnormalities**

Vital sign (unit)	Notable abnormalities
Systolic blood pressure (mmHg)	$\geq 140 \text{ mmHg}$ or $< 90 \text{ mmHg}$
Diastolic blood pressure (mmHg)	$\geq 90 \text{ mmHg}$ or $< 60 \text{ mmHg}$
Pulse (bpm)	$> 100 \text{ bpm}$ or $< 60 \text{ bpm}$

#### 2.8.4.3 Physical examination

Summary statistics will be provided for physical examination by visit.

#### 2.8.4.4 Height and weight

Summary statistics will be provided for height and weight captured at screening.

#### 2.8.4.5 Pregnancy and assessment of fertility

A serum  $\beta$ -hCG test will be performed in all women at Screening.

Urine pregnancy test will be performed at various visits as indicated in the assessment schedule

Summaries will be provided for both the above tests as other safety measures.

#### 2.8.4.6 Tolerability of secukinumab

Tolerability will be assessed by AEs, laboratory values and injection site reactions and summarized accordingly.

### 2.9 Pharmacokinetic endpoints

Not applicable

### 2.10 PD and PK/PD analyses

Not applicable

### 2.11 Patient-reported outcomes

#### Patient's global assessment of disease activity

Patient's global assessment of disease activity, measured on a VAS scale will be analyzed using an ANCOVA model with factors treatment, country and diagnosis (PsA or axSpA) and

with covariate baseline measurement of the global assessment of disease activity. The adjusted (LS-) mean difference will be calculated as a point estimate together with its corresponding 95% confidence interval and p-value.

### **Patient's global assessment of heel enthesiopathy activity**

Patient's global assessment of heel enthesiopathy, measured on a VAS scale will be analyzed using an ANCOVA model with factors treatment, country and diagnosis (PsA or axSpA) and with covariate baseline measurement of the global assessment of heel enthesiopathy. The adjusted (LS-) mean difference will be calculated as a point estimate together with its corresponding 95% confidence interval and p-value.

### **Short Form-36 Physical Component Summary (SF-36 PCS) or SF-36v2**

The score of the SF-36 or SF-36v2 will be analyzed using an ANCOVA model with factors treatment, country and diagnosis (PsA or axSpA) and with covariate baseline value of SF-36 or SF-36v2. The adjusted (LS-) mean difference will be calculated as a point estimate together with its corresponding 95% confidence interval and p-value.

[figure not shown]

[figure not shown]
### **Bath ankylosing spondylitis disease activity index (BASDAI)**

BASDAI will be summarized descriptively for axSpA patients. Summary statistics will include relative and absolute frequencies.

## **2.12 Biomarkers**

Not applicable

## **2.14 Interim analysis**

Once all data until/including Week 24 (containing the primary and secondary endpoints) are complete and clean, the database for that study period will be locked and analyzed. The results may be published or made available to personnel involved in data collection of this study prior to database lock of the complete study period until Week 52.

The details of the Week 24 analyses will be mentioned in TFL Shells. Additional SAP for Week 24 analyses will be written if required.

## **3 Sample size calculation**

The primary endpoint of this trial is the percentage of patients with resolution of Achilles tendon enthesitis assessed by application of firm pressure with the pulp of the thumb by the physician at Week 24. The sample size calculation is based on the same enthesitis assessment we performed within the FUTURE 2 PsA trial (CAIN457F2312) in the form of the LEI which is composed of three different enthesial sites (Lateral epicondyle, left and right; medial femoral condyle, left and right; Achilles tendon insertion, left and right). Within this trial, the resolution of enthesitis amongst those patients with these symptoms at Baseline has been assessed for Week 24:

Week 24, the end of the placebo-controlled phase:

- Secukinumab (300 mg): 48.2% of patients.
- Secukinumab (150 mg): 42.2% of patients.
- Placebo: 21.5% of patients.

In addition to these clinical data we can make the following assumptions:

- There is no difference in response to secukinumab between the different enthesis sites assessed as part of the LEI in the FUTURE 2 trial. Therefore we do not expect a different response when we only assess the Achilles tendon insertion.
- There is no difference in secukinumab response rates regarding resolution of enthesitis between PsA and axPsA patients. Therefore we pool the analysis for both diseases.

A total of 89 patients per arm are required to achieve 90% power to detect a difference on a two-sided, 2.5% significance level, if the true response rates are 45% under secukinumab and 21% under placebo. To account for some drop-outs and other protocol violations, 100 patients per arm = 200 patients total should be randomized into this trial.

For the comparison within the 2 subgroups of PsA and axPsA patients, which will consist of 50% of the total study population each, the trial will have about 46% power with regard to the primary endpoint.

No sample size justification is provided for secondary analyses, hence results from secondary analyses should be interpreted carefully.

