9.8 Sample size calculation

The primary endpoint of this trial is the percentage of patients with resolution of Achilles tendon enthesitis assessed by application of firm pressure with the pulp of the thumb by the physician at Week 24. The sample size calculation is based on the same enthesitis assessment we performed within the FUTURE 2 PsA trial (CAIN457F2312) in the form of the LEI which is composed of three different enthesial sites (Lateral epicondyle, left and right; Medial femoral condyle, left and right; Achilles tendon insertion, left and right). Within this trial, the resolution of enthesitis amongst those patients with these symptoms at Baseline has been assessed for Week 24:

Week 24, the end of the placebo-controlled phase:

- Secukinumab (300 mg): 48.2% of patients.
- Secukinumab (150 mg): 42.2% of patients.
- Placebo: 21.5% of patients.

In addition to these clinical data we can make the following assumptions:

- There is no difference in response to secukinumab between the different enthesial sites assessed as part of the LEI in the FUTURE 2 trial. Therefore we do not expect a different response when we only assess the Achilles tendon insertion.
- There is no difference in secukinumab response rates regarding resolution of enthesitis between PsA and axPsA patients. Therefore we pool the analysis for both diseases.

A total of 89 patients per arm are required to achieve 90% power to detect a difference on a two-sided, 5% significance level, if the true response rates are 45% under secukinumab and 21% under placebo. To account for some drop-outs and other protocol violations, 100 patients per arm = 200 patients total should be recruited into this trial.

For the comparison within the 2 subgroups of PsA and axSpA patients, which will consist of approximately 50% of the total study population each, the trial will have about 58% power with regard to the primary endpoint.

10 Ethical considerations

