## 2 Statistical methods

### 2.1 Data analysis general information

The analysis will be conducted by Novartis on all patient data after database lock for the respective trial periods. Any data analysis carried out independently by the investigator should be submitted to Novartis before publication or presentation.

Analysis datasets and statistical outputs will be produced using the most recent SAS® Version 9.4 (SAS Institute Inc., Cary, NC, USA), and stored in Novartis global programming & statistical environment (GPS).

Following the Week 24 database lock, the Sponsor will be unblinded to treatment assignment. Once all data until/including Week 24 (containing the primary and secondary endpoints) are complete and clean, the database for that study period may be locked and analyzed.

Continuous variables will be summarized by number of patients, mean, standard deviation, minimum, median and maximum. Categorical variables will be summarized by absolute and relative frequencies. Summary statistics will also be presented graphically wherever applicable.

If not otherwise specified, p-values and confidence intervals will be two-sided. Unless otherwise stated, the level of significance will be set to 5% (two-sided, family-wise type-I-error).

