### 2.5.2 Statistical hypothesis, model, and method of analysis

The null hypothesis to be rejected is that the odds of response Week 24 are equal in both treatment groups. The corresponding alternative hypothesis is that the odds of response at Week 24 are higher under secukinumab compared to placebo.

In other words: Let  $p_j$  denote the proportion of responders at Week 24 for treatment group  $j$ ,  $j=0, 1$ , where

- 0 corresponds to placebo
- 1 corresponds to secukinumab

The following hypotheses will be tested:

$H_0: (p_1 / (1-p_1)) / (p_0 / (1-p_0)) = 1$  versus  $H_1: (p_1 / (1-p_1)) / (p_0 / (1-p_0)) \neq 1$

In other words,  $H_1$ : The odds ratio of achieving a response at Week 24 for secukinumab vs Placebo is different from 1.

The hypotheses can also be re-written as a difference of proportions as follows:

In statistical terms,  $H_0: p_1 = p_0$ ,  $H_1: p_1 \neq p_0$ , i.e.

$H_1$ : The difference of proportions at Week 24 for secukinumab vs Placebo is different from 0.

The primary analysis will be performed comparing treatments with respect to the primary efficacy variable in a logistic regression model with the factors treatment, country and

[figure not shown]
stratification factor diagnosis (PsA or axSpA). The odds ratio and its 95% confidence interval (CI) and p-value will be presented comparing secukinumab to placebo at Week 24.

The study is said to be positive/declared as success if the lower limit of 95% CI of odds ratio is greater than 1.

The primary endpoint (percentage of patients with resolution of Achilles tendon enthesitis) will additionally be analyzed separately for the subgroups of patients with PsA or axSpA, using the same model as for the respective pooled, overall population tests (except for the stratification factor). Those two subgroup analyses are included in the confirmatory testing strategy. The primary model will also be recalculated with the stratification factor included as well as with respective term for a strata\*treatment interaction.

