### Testing strategy

The primary endpoint will be confirmatorily tested in the pooled, overall population as well as in the two complementary subgroups of patients with PsA or axSpA.

If the null hypotheses has been rejected for the overall population, it will then be tested for both subgroups simultaneously, both at the significance level 0.05. If the null-hypothesis is false for the overall population, it can logically not be true for both complementary subgroups.

Therefore both subgroups can be tested at the same significance level  $\alpha = 0.05$  without any further adjustments for multiplicity of subgroups. This procedure provides strong control of the familywise type-I-error at  $\alpha = 0.05$ .

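### SAP Section 3 states a two-sided 2.5% level and about 46% subgroup power, while every decision rule and protocol 9.8 use two-sided 5%, for which the protocol gives about 58%

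*SAP*

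**What the plan says.** SAP Section 3: "A total of 89 patients per arm are required to achieve 90% power to detect a difference on a two-sided, 2.5% significance level", with true response rates of 45% on secukinumab and 21% on placebo. It adds an allowance for drop-outs and protocol violations, so that "100 patients per arm = 200 patients total should be randomized into this trial". On the PsA and axSpA subgroups it says: "which will consist of 50% of the total study population each, the trial will have about 46% power".

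Protocol 9.8 has the same rates, 89 per arm, 90% power and total of 200. It plans to "detect a difference on a two-sided, 5% significance level", and for the subgroups says "the trial will have about 58% power with regard to the primary endpoint".

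The SAP's rules for the analysis itself are:

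- Section 2.1: "the level of significance will be set to 5% (two-sided, family-wise type-I-error".
- Section 2.5.2: "The study is said to be positive/declared as success if the lower limit of 95% CI of odds ratio is greater than 1".
- Testing strategy within 2.5.2: the two subgroups are tested "both at the significance level 0.05", with no further adjustment. Protocol 9.5.1.7 says the same.

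SAP Section 4 records no change from the protocol-specified analyses.

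**The concern.** One design cannot need the same number of patients, for the same power and rates, at two different significance levels under one method. Nor can the subgroups have both 46% and 58% power. No rule in either document tests anything at 2.5%, so the 2.5% in SAP Section 3 corresponds to no planned test.

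SAP Section 1 describes the document as a draft of the study report's section on statistical methods and sample size. Left alone, the report would give a planned significance level that contradicts its own success rule. The subgroup tests belong to the confirmatory strategy. A planned power of 46% describes each as less likely than not to succeed, which is the wrong background for reading a non-significant subgroup result.

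**Working it through.** **Inputs.** Rates p1 = 0.45 and p0 = 0.21, and 89 per arm for 90% power (SAP 3 and protocol 9.8). Allocation is 1:1 (SAP 1.1). Each subgroup is half the study: about 44 per arm if taken from the 89, or 50 per arm if taken from the 100 randomized. Neither document names the test method or the subgroup size per arm, so several standard methods were tried.

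**Formulas.** Let S0 = √(2 × 0.33 × 0.67 / n), where 0.33 is the mean rate, and S1 = √((0.45 × 0.55 + 0.21 × 0.79) / n). The critical value z is 1.960 at two-sided 5% and 2.241 at two-sided 2.5%.

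- Unpooled: power = Φ(0.24 / S1 − z)
- Pooled: power = Φ((0.24 − z·S0) / S1)
- Continuity-corrected: power = Φ((0.24 − 1/n − z·S0) / S1)
- Fisher's exact test and the Wald test of the log odds ratio: exact enumeration of the two binomials, without covariates

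**Step 1: can the SAP's figures be reproduced at 2.5%?** Each can be approached singly.

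- Unpooled, n = 89: S1 = 0.06815, so Φ(0.24/0.06815 − 2.241) = Φ(1.280) = 90.0%. This fits the stated 90%.
- Continuity-corrected, n = 44: S0 = 0.10025 and S1 = 0.09693, so Φ((0.21727 − 0.22470)/0.09693) = Φ(−0.077) = 46.9%. This is close to the stated 46%.

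They do not come from one method:

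| Method, two-sided 2.5% | 89 per arm | 44 per arm | 50 per arm |
|---|---|---|---|
| Continuity-corrected | 85.0% | 46.9% | 54.0% |
| Fisher | 85.4% | 49.0% | 55.6% |
| Wald log odds ratio | 88.2% | 55.9% | 62.5% |
| Pooled | 88.6% | 56.3% | 62.6% |
| Unpooled | 90.0% | 59.3% | 65.5% |

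The method that gives 90% overall gives 59% in a subgroup, and the method closest to 46% gives 85% overall. With 50 per arm, no method gives 46%.

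**Step 2: the same calculation at 5%.**

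| Method, two-sided 5% | 89 per arm | 44 per arm | 50 per arm |
|---|---|---|---|
| Continuity-corrected | 90.8% | 58.5% | 65.3% |
| Fisher | 91.0% | 59.9% | 66.2% |
| Wald log odds ratio | 93.2% | 68.1% | 72.2% |
| Pooled | 93.2% | 67.3% | 73.0% |
| Unpooled | 94.1% | 69.7% | 75.2% |

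Continuity-corrected, n = 44: Φ((0.21727 − 0.19649)/0.09693) = Φ(0.214) = 58.5%. With 90.8% at 89 per arm, this is consistent with both protocol figures.

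**Step 3: what separates 46% from 58%?** On one method and size (continuity-corrected, 44 per arm), changing only the level moves power from 46.9% to 58.5%. The level alone is enough to explain the gap. That basis is inferred from the figures.

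**Step 4: does 89 per arm identify the level?** The smallest n for 90% power is 76 to 87 per arm at 5% (unpooled 76, pooled 79, Fisher 86, continuity-corrected 87). At 2.5% it is 90 to 102 (unpooled 90, pooled 94, Fisher 100, continuity-corrected 102). So 89 is sufficient at 5% on every method and just short at 2.5% on every method, but it is the exact requirement of none. The decision rules settle the level; 89 does not.

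**Step 5: could drop-outs bring the power down to 46%?** As an illustrative assumption, take 11% drop-out in both arms (11 of 100, from the gap between 89 and 100), all counted as non-responders in the full analysis set. The rates become 0.45 × 0.89 = 40.1% and 0.21 × 0.89 = 18.7%. With 50 per arm at 5%, power is 56.8% (continuity-corrected) to 67.4% (unpooled), still about 11 points above 46%.

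**The case against.** Five points can be made for the plan.

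1. **Nothing operational changes.** The tests run at 5%, 200 patients are randomized either way, and 89 per arm is enough at 5%. A non-significant subgroup is inconclusive at 46% or at 58%. This is true and limits the weight of the point, but a wrong stated level and power in confirmatory design text still need correcting.

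2. **2.5% at 89 per arm is not impossible.** The unpooled formula gives 90.0% there. That stands, which is why the case rests on the contradiction between documents and with the SAP's own rules. The same formula gives 59.3% in the subgroups, so it does not rescue the 46%.

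3. **A divided level could be behind the figures.** Splitting the level between the two subgroups, the pooled formula with 44 per arm gives 45.7% at 1.25% and 56.3% at 2.5%, close to both stated powers. It is thus a second candidate for how the numbers arose. It cannot describe the plan, because both documents test each subgroup at an undivided 0.05, and the pooled formula gives 88.6%, not 90%, at 89 per arm and 2.5%.

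4. **The protocol's 58% may itself be doubtful.** It matches about 44 per arm, whereas half of 200 is 50 per arm, for which power at 5% is 65% to 75%. This stands, and the 58% should be confirmed before it is copied.

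5. **The drop-out scenario is not a bound.** Drop-out concentrated on secukinumab would lower power further, and drop-outs who had already responded count as responders. It is an illustration, and the conclusion does not depend on it.

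**Conclusion.** The concern holds. The two-sided 2.5% level in SAP Section 3 contradicts the SAP's own decision rules and protocol 9.8, and the 46% is not the power of the planned subgroup tests. At the stated rates and two-sided 5%, the lowest figure from any method tried is 58.5%, so 46% is at least 12 points low (58.5 − 46 = 12.5). With 50 per arm the gap is 19 to 29 points (65.3 − 46 and 75.2 − 46).

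This rests on the stated 45% and 21%, equal arms within each subgroup, and no covariate adjustment. How the sponsor obtained 46% and 58% remains inference. The error understates power, and the sample size and error control are unaffected. It should be fixed because the text is meant to pass into the study report.

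**What to change.** In SAP Section 3, replace 2.5% with 5%, and replace the 46% with the subgroup power at two-sided 5%: about 58%, to agree with protocol 9.8, if the sponsor confirms how that figure was obtained.

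In both documents, state beside the figure the test method and the number per arm in each subgroup. A continuity-corrected test with about 44 per arm reproduces 58%, but should be written in only if confirmed. If 50 per arm was intended, both documents need the same restated value, which at the stated rates lies between 65% and 75% depending on the method, before any dilution by drop-outs.

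The cost is two figures in SAP Section 3 and one clause in each document. No test and no sample size changes.
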